3.10.4 Palliative Local Therapy

- Palliative and supportive care for disease related symptoms may be offered to all subjects on the trial after the DLT evaluation period. Limited radiation therapy or surgery to control isolated lesions is permitted for subjects who have investigator assessed clinical benefit following consultation with the BMS Medical Monitor.
- Subjects should not receive study treatment during radiation as the potential for overlapping toxicities with radiotherapy and BMS-986156, or combination of BMS-986156 and nivolumab currently is not known. Anecdotal data suggest that radiotherapy administered to subjects while receiving nivolumab therapy is tolerable. However, because concurrent radiotherapy and immunotherapies in cancer have not been formally evaluated, in cases where palliative radiotherapy is required for a tumor lesion, then BMS-986156 alone or BMS-986156 in combination with nivolumab should be withheld for at least 1 week before, during, and 1 week after radiation. Subjects should be closely monitored for any potential toxicity during and after receiving radiotherapy, and AEs related to radiotherapy should resolve to Grade 1 prior to resuming study therapy.
- Subjects who have received palliative local therapy will be documented as having had disease progression for the purpose of efficacy analyses.

3.11 Discontinuation of Subjects Following Any Treatment with Study Drug

Subjects MUST discontinue investigational product (IP) (and non-IP at the discretion of the Investigator) for any of the following reasons:

- Subject's request to stop study treatment and/or participation in the study
- Any clinical AE, laboratory abnormality or intercurrent illness which, in the opinion of the Investigator, indicates that continued participation in the study is not in the best interest of the subject
- Termination of the study by BMS
- Loss of ability to freely provide consent through imprisonment or involuntarily incarceration for treatment of either a psychiatric or physical (e.g., infectious disease) illness
- Pregnancy

- Documented and confirmed disease progression as defined by RECIST (see [Appendix 3](#)) unless subject meets criteria for treatment beyond progression (Section 3.11.1)
- Clinical deterioration while receiving active study therapy that in the opinion of the Investigator indicates that continued participation in the study is not in the best interest of the subject
- Discretion of the Investigator
- Inability to comply with the protocol requirements
- Protocol defined reasons for discontinuation (see [Section 4.3.6](#)).

In the case of pregnancy, the Investigator must immediately notify the BMS Medical Monitor/Designee of this event. In most cases, the study drug will be permanently discontinued in an appropriate manner. If the Investigator determines a possible favorable benefit/risk ratio that warrants continuation of study drug, a discussion between the Investigator and the BMS Medical Monitor/Designee must occur.

All subjects who discontinue IP should comply with protocol specified follow-up procedures as outlined in [Section 3.3](#). The only exception to this requirement is when a subject withdraws consent for all study procedures including post-treatment study follow-up or loses the ability to consent freely (e.g., is imprisoned or involuntarily incarcerated for the treatment of either a psychiatric or physical illness).

If study drug is discontinued prior to the subject's completion of the study, the reason for the discontinuation must be documented in the subject's medical records and entered on the appropriate CRF page.

3.11.1 Treatment Beyond Disease Progression

As described in [Section 1.1.3](#) accumulating evidence indicates a minority of subjects with solid tumors treated with immunotherapy may derive clinical benefit despite initial evidence of PD. Subjects will be permitted to continue on treatment beyond initial RECIST v1.1 (see [Appendix 3](#)) defined PD, as long as they meet the following criteria:

- Investigator-assessed clinical benefit, and do not have rapid disease progression
- Continue to meet all other study protocol eligibility criteria
- Tolerance of study drug
- Stable performance status
- Treatment beyond progression will not delay an imminent intervention to prevent serious complications of disease progression (eg, CNS metastases)
- Subject provides written informed consent prior to receiving any additional nivolumab or BMS-986156 treatment, using an ICF describing any reasonably foreseeable risks or discomforts, or other alternative treatment options
- Absence of signs or symptoms indicating disease progression

The assessment of clinical benefit should take into account whether the subject is clinically deteriorating and unlikely to receive further benefit from continued treatment. All decisions to continue treatment beyond initial progression must be discussed with the BMS Medical Monitor

and an assessment of the risk/benefit of continuing with study therapy must be documented in the study records. Subjects will be re-consented to explain the rationale for this ongoing treatment.

3.11.1.1 Discontinuation Due to Further Progression (Confirmed Progression)

Subjects should discontinue study therapy upon further evidence of further progression, defined as an additional 10% or greater increase in tumor burden volume from time of initial progression (including all target lesions and new measurable lesions).

The tumor burden volume from time of initial progression should be used as the reference baseline for comparison with the post-progression assessment.

Any new lesion considered non-measurable at the time of initial progression may become measurable and therefore must be included in the tumor burden measurement as follows:

New lesions are considered measurable at the time of initial progression if the longest diameter is at least 10 mm (except for pathological lymph nodes, which must have a short axis of at least 15 mm).

For statistical analyses that include the investigator-assessed progression date, subjects who continue treatment beyond initial investigator-assessed, RECIST v1.1-defined progression will be considered to have investigator-assessed progressive disease at the time of the initial progression event.

3.11.1.2 Assessment Schedule for Subjects with Post-progression Treatment

Subjects should continue to receive monitoring according to the On-Treatment Assessments in [Section 5.3](#). Radiographic assessment by computerized tomography (CT; preferred) or MRI described in [Section 5](#) is required when subjects continue post-progression treatment. For subjects that discontinue post-progression treatment with study therapy, no additional radiographic assessments will be required.

3.12 Post Study Drug Follow up

Post-study follow-up is of critical importance and is essential to preserving subject safety and the integrity of the study. Subjects who discontinue study drug must continue to be followed per the Safety Follow-up (approximately 100 days).

3.12.1 Withdrawal of Consent

Subjects who request to discontinue study drug will remain in the study and must continue to be followed for protocol specified follow-up procedures. The only exception to this is when a subject specifically withdraws consent for any further contact with him/her or persons previously authorized by subject to provide this information. Subjects should notify the Investigator of the decision to withdraw consent from future follow-up in writing, whenever possible. The withdrawal of consent should be explained in detail in the medical records by the Investigator, as to whether the withdrawal is from further treatment with study drug only or also from study procedures and/or post treatment study follow-up, and entered on the appropriate CRF page. In the event that vital status (whether the subject is alive or dead) is being measured, publicly available information

should be used to determine vital status only as appropriately directed in accordance with local law.

3.12.2 Lost to Follow-up

All reasonable efforts must be made to locate subjects to determine and report their ongoing status. This includes follow-up with persons authorized by the subject as noted above. Lost to follow-up is defined by the inability to reach the subject after a minimum of three documented phone calls, faxes, or emails as well as lack of response by subject to one registered mail letter. All attempts should be documented in the subject's medical records. If it is determined that the subject has died, the site will use permissible local methods to obtain the date and cause of death.

If Investigator's use of third-party representative to assist in the follow-up portion of the study has been included in the subject's informed consent, then the Investigator may use a Sponsor-retained third-party representative to assist site staff with obtaining subject's contact information or other public vital status data necessary to complete the follow-up portion of the study. The site staff and representative will consult publicly available sources, such as public health registries and databases, in order to obtain updated contact information. If after all attempts, the subject remains lost to follow-up, then the last known alive date as determined by the Investigator should be reported and documented in the subject's medical records.

4 TREATMENTS

All protocol-specified investigational and non-IPs are considered study drug:

4.1 Study Treatments

Product description and storage information is described in [Table 4.1-1](#). Preparation and administration instructions will be provided separately via site training materials.

For study drugs not provided by BMS and obtained commercially by the site, storage should be in accordance with the package insert, summary of product characteristics (SmPC), or similar documentation.

Table 4.1-1: Study Drugs for CA009002

Product Description Class and Dosage Form	Potency	IP/Non-IP	Blinded or Open Label	Packaging/Appearance	Storage Conditions (per Label)
BMS-986156 injection	100 mg/vial (10 mg/mL)	IP	Open	Clear to opalescent colorless to pale yellow liquid. May contain particles	2 to 8°C. Protect from light
Nivolumab injection	100 mg/vial (10 mg/mL)	IP	Open	Clear to opalescent colorless to pale yellow liquid. May contain particles	2 to 8°C. Protect from light and freezing

Abbreviation: IP, investigational product

4.1.1 Investigational Product

An IP, also known as investigational medicinal product in some regions, is defined a pharmaceutical form of an active substance or placebo being tested or used as a reference in a clinical study, including products already with a marketing authorization but used or assembled (formulated or packaged) differently than the authorized form, or used for an unauthorized indication, or when used to gain further information about the authorized form.

The IP should be stored in a secure area according to local regulations. It is the responsibility of the Investigator to ensure that IP is only dispensed to study subjects. The IP must be dispensed only from official study sites by authorized personnel according to local regulations.

In this protocol, IPs are: BMS-986156 and nivolumab.

4.1.2 Non-investigational Product

Other medications used as support or escape medication for preventative, diagnostic, or therapeutic reasons, as components of the standard of care for a given diagnosis, may be considered as non-IPs.

In this protocol, non- IP(s) is/are: Not applicable for this study.

4.1.3 Storage and Dispensing

The product storage manager should ensure that the study drug is stored in accordance with the environmental conditions (temperature, light, and humidity) as determined by BMS. If concerns regarding the quality or appearance of the study drug arise, the study drug should not be dispensed and contact BMS immediately.

Non-study drug not supplied by BMS will be stored in accordance with the package insert.

IP documentation (whether supplied by BMS or not) must be maintained that includes all processes required to ensure drug is accurately administered. This includes documentation of drug storage, administration and, as applicable, storage temperatures, reconstitution, and use of required processes (e.g., required diluents, administration sets).

For non-IP, if marketed product is utilized, it should be stored in accordance with the package insert, SmPC, or similar.

For treatment visits where both BMS-986156 and nivolumab are administered, nivolumab will be administered first for 30 minutes followed by BMS-986156 at least 30 minutes after completion of the nivolumab infusion. Further details regarding preparation and administration will be provided separately in site/pharmacy training materials

4.2 Method of Assigning Subject Identification

This is an open-labeled study. All subjects must be assigned a subject number upon providing signed written informed consent. During the Screening visit, the investigative site will call into the enrollment option of the IVRS designated by BMS for assignment of a 5-digit subject number that will be unique across all sites. Enrolled subjects, including those not dosed, will be assigned sequential subject numbers [REDACTED]. The patient

identification number (PID) will ultimately be comprised of the site number and subject number. For example, the first subject screened (e.g., enrolled) at site number 1, will have a PID [REDACTED]. Specific instructions for using IVRS will be provided to the investigational sites in a separate document.

Once it is determined that the subject meets the eligibility criteria following the Screening visit, the investigative site will call the IVRS within 3 days prior to the first study drug administration for the subject to be either:

- Assigned to a part (Part A or Part B) and dose cohort in the dose escalation portion of the study
- Assigned to a part (Part C, D, or E F) and dose cohort in the dose expansion portion of the study.

During dose escalation, all subjects will be assigned to Part A until the decision is made to start the combination with nivolumab at n-1 dose level. Subsequently, treatment in Part B will be initiated and escalation in the 2 parts will occur in parallel. Treatment assignments for subjects eligible for both Part A and Part B will alternate between the 2 parts, with consecutively treated subjects assigned to different parts through IVRS whenever possible. If there are no openings available in the part to which the subject would be assigned by this algorithm, then the subject will be assigned to the next open part/cohort.

During dose escalation (Part A and Part B), subjects who are not evaluable for DLT determination may be replaced. Replacement subjects will be assigned to the same part (Part A or Part B) and dose, but will be assigned a new subject number.

Subjects in expansion cohorts in Parts C and D and E may be added if adequate paired pre-treatment and on-treatment biopsy specimens are not obtained. The replacement subject will receive the same treatment as the subject being replaced but a new subject number will be assigned.

Escalation and expansion may be open in parallel. Once expansion is open subjects eligible for parts C and D and E based on tumor type, may be assigned to any open cohort.

4.3 Selection and Timing of Dose for Each Subject

Each subject will be assigned to a specific dose level as listed in [Section 4.2](#) in sequential order during dose escalation. Subjects in cohort expansion will be treated at the MTD, the MAD, or at an alternate dose(s), as agreed upon by the Investigators and the Sponsor.

Nivolumab will be administered as flat doses in cohorts B and D at 240 mg and in cohort E, at 480 mg. There will be no dose escalations or reductions of nivolumab allowed once assigned. Subjects may be dosed no less than 12 days from the previous dose. There are no pre-medications recommended for nivolumab on the first cycle. If an acute infusion reaction is noted, the subjects should be managed according to [Section 4.3.7](#).

BMS-986156 will be administered as flat dosing at the doses listed in [Section 1.1.1](#).

4.3.1 Dose-limiting Toxicities

AEs will be graded according to the NCI CTCAE v4.03.

Non-hematologic Dose-limiting Toxicity (DLT)

A. Hepatic Non-hematologic DLT

Any one of the following study drug-related events will be considered a hepatic DLT:

- Any Grade ≥ 3 elevation of AST, ALT, or total bilirubin
- Grade 2 AST or ALT with symptomatic liver inflammation (e.g., right upper quadrant tenderness, jaundice, pruritus)
- AST or ALT $> 3 \times$ ULN and concurrent total bilirubin $> 2 \times$ ULN without initial findings of cholestasis (elevated serum ALP (e.g., findings consistent with Hy's law or FDA definition of potential drug-induced liver injury or pDILI). Note that this special category of DLT uses ULN rather than CTC Grade for definition

B. Non-hepatic Non-hematologic DLT

Any of the following events will be considered a Non-Hepatic Non-Hematologic DLT:

- Any Grade 2 drug-related uveitis or eye pain or blurred vision that does not respond to topical therapy and does not improve to Grade 1 severity ≤ 2 weeks OR requires systemic treatment
- Grade 3 drug-related uveitis, pneumonitis, bronchospasm, neurologic toxicity, hypersensitivity reaction, or infusion reaction of any duration requires discontinuation
- Any Grade 3 or greater non-dermatologic, non-hepatic non-hematologic study drug-related toxicity will be considered a dose-limiting toxicity with the following specific EXCEPTIONS:
 - Grade 3 or grade 4 electrolyte abnormalities that are not complicated by associated clinical adverse experiences, last ≤ 48 hours and either resolve spontaneously or respond to conventional medical intervention
 - Grade 3 nausea, vomiting or diarrhea that lasts less than 48 hours, and either resolves spontaneously or responds to conventional medical intervention
 - Isolated Grade 3 elevation of amylase or lipase not associated with clinical or radiographic evidence of pancreatitis
 - Isolated Grade 3 fever not associated with hemodynamic compromise (eg, hypotension, clinical or laboratory evidence of impaired end-organ perfusion)
 - Grade 3 endocrinopathy that is well controlled by hormone replacement
 - Grade 3 tumor flare (defined as pain, irritation, or rash that localizes to sites of known or suspected tumor)
 - Grade 3 fatigue for ≤ 7 days
 - Grade 3 infusion reaction that returns to Grade 1 in ≤ 6 hours

C. Dermatologic DLT

- Grade 3/4 rash if no improvement (i.e. resolution to \leq Grade 1) after a 1-2 week infusion delay. Subjects who have not experienced a Grade 3 drug-related skin AE may resume treatment in the presence of Grade 2 skin toxicity.

D. Hematologic DLT (Study Drug-related)

- Grade 4 neutropenia \geq 5 days in duration
- Grade 4 thrombocytopenia or Grade 3 thrombocytopenia with clinically significant bleeding, or any requirement for platelet transfusion
- Grade 4 anemia not explained by underlying disease
- Grade 4 febrile neutropenia
- Grade 3 febrile neutropenia that lasts > 48 hours
- Grade \geq 3 hemolysis (ie, requiring transfusion or medical intervention such as steroids)

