4.3.5 Criteria to Resume Treatment

Subsequent dosing with study therapy may resume once drug-related non-DLT AEs resolve to Grade 1 or baseline.

Subjects experiencing AEs not meeting criteria for permanent discontinuation as outlined in [Section 4.3.6](#) may resume treatment with study medication under the following criteria:

- Subjects may resume treatment with study drug when the drug-related AE(s) resolve to Grade ≤ 1 or baseline value with the following exceptions:
 - Subjects may resume treatment in the presence of Grade 2 fatigue;
 - Subjects who have not experienced a Grade 3 drug-related skin AE may resume treatment in the presence of Grade 2 skin toxicity;
 - Subjects with Grade 2 uveitis or eye pain or blurred vision not meeting DLT criteria ([Section 4.3.1](#)) must resolve to baseline prior to resuming study therapy;
 - Drug-related pulmonary toxicity, diarrhea, or colitis, must have resolved to baseline before treatment is resumed;
 - Drug-related endocrinopathies adequately controlled with only physiologic hormone replacement may resume treatment.

If the criteria to resume treatment are met, the subject should restart treatment at the next scheduled time point per protocol.

The consideration to re-initiate study therapy under these exceptions will be made on a case by case basis after considering the overall benefit/risk profile and in consultation between the Investigator and the study sponsor. Any AE with clinical risk will be assessed on a case by case basis with the Investigator and the BMS Medical Monitor to determine the risks and benefits of continuing on therapy following resolution versus discontinuing therapy permanently.

If treatment with study medication is delayed > 6 weeks, the subject must be permanently discontinued from study therapy, except as specified in Section 4.3.6.

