4.3.6 Guidelines for Permanent Discontinuation

Subjects will be required to permanently discontinue both study drugs for the following AEs:

- Any drug related AE occurring at any time that meets DLT criteria as outlined in [Section 4.3.1](#) will require permanent discontinuation with the following **exceptions**:
 - a) Grade 3 diarrhea, nausea, vomiting, or abdominal pain that returns to grade 1 or baseline within 3 days with medical intervention;
 - b) Grade 3 pruritus or rash that returns to grade 1 or baseline within 7 days or baseline with medical intervention;
 - c) Grade 4 electrolyte abnormalities that \leq 72 hours in duration;
 - d) Grade 4 neutropenia \leq 5 days in duration;
 - e) Grade 4 increase in amylase or lipase that is not associated with clinical or radiographic evidence of pancreatitis;
 - f) Grade 4 lymphopenia \leq 5 days in duration.
- Any dosing delay lasting > 6 weeks will be cause for permanent discontinuation. Extensions to the period of dose delays may be granted for individual subjects on a case by case basis after specific consultation and agreement between the Investigator and BMS Medical Monitor in settings where benefit/risk may justify continued study therapy (e.g., subject deriving clinical benefit who requires prolonged steroid taper for management of non-DLT irAEs, or experiences delays for management of a non-drug-related AE).
- Accordingly, dosing delays to allow for prolonged steroid tapers to manage drug-related AEs are allowed. Additionally, dosing delays > 6 weeks that occur for non-drug-related reasons may be allowed if approved by the BMS Medical Monitor.
- Prior to re-initiating treatment in a subject with a dosing delay lasting > 6 weeks, the BMS Medical Monitor must be consulted.
- Tumor assessments should continue as per protocol even if dosing is delayed.

All subjects who discontinue IP should comply with protocol specified follow-up procedures as outlined in [Section 3.3](#). The only exception to this requirement is when a subject withdraws consent for all study procedures including post-treatment study follow-up or loses the ability to consent freely (e.g., is imprisoned or involuntarily incarcerated for the treatment of either a psychiatric or physical illness).

If study treatment is discontinued prior to the subject's completion of the study, the reason for the discontinuation must be documented in the subject's medical records and entered on the appropriate CRF page.

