4.3.7 Treatment of Drug-related Infusion Reactions

Since BMS-986156 and nivolumab contain only human immunoglobulin protein sequences, it is unlikely to be immunogenic and induce infusion or hypersensitivity reactions. However, if such a reaction were to occur, it might manifest with fever, chills, rigors, headache, rash, pruritus, arthralgias, hypo- or hypertension, bronchospasm, or other symptoms. All Grade 3 or 4 infusion

reactions should be reported within 24 hours to the BMS Medical Monitor and reported as an SAE if criteria are met. Infusion reactions should be graded according to NCI CTCAE v4.03 guidelines.

Treatment recommendations are provided below and may be modified based on local treatment standards and guidelines as appropriate:

For Grade 1 symptoms: (Mild reaction; infusion interruption not indicated; intervention not indicated)

Remain at bedside and monitor subject until recovery from symptoms. The following prophylactic premedications are recommended for future infusions: diphenhydramine 50 mg (or equivalent) and/or acetaminophen/paracetamol 325 to 1000 mg at least 30 minutes before additional study drug administrations.

For Grade 2 symptoms: Moderate reaction requires therapy or infusion interruption but responds promptly to symptomatic treatment [e.g., antihistamines, non-steroidal anti-inflammatory drugs, narcotics, corticosteroids, bronchodilators, IV fluids]; prophylactic medications indicated for ≤ 24 hours.

- Stop the nivolumab infusion, begin an IV infusion of normal saline, and treat the subject with diphenhydramine 50 mg IV (or equivalent) and/or paracetamol 325 to 1000 mg (acetaminophen); monitor subject until resolution of symptoms.
- Bronchodilator or corticosteroid therapy may also be administered as appropriate.
- The infusion may be restarted at 50% of the original infusion rate when symptoms resolve; if no further complications ensue after 30 minutes, the rate may be increased to 100% of the original infusion rate. Monitor subject closely.
- The amount of study drug infused must be recorded on the CRF.
- If symptoms recur, then no further nivolumab, as the case may be, will be administered at that visit.

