- The following prophylactic premedications are recommended for future infusions: diphenhydramine 50 mg (or equivalent) and/or paracetamol 325 to 1000 mg (acetaminophen) should be administered at least 30 minutes before additional nivolumab administrations. If necessary, corticosteroids (up to 25 mg of SoluCortef or equivalent) may be used.

Late-occurring symptoms: In the case of late-occurring hypersensitivity symptoms (e.g., appearance of a localized or generalized pruritus within 1 week after treatment), symptomatic treatment may be given (eg, oral antihistamine, or corticosteroids).

For Grade 3 or Grade 4 symptoms (Severe reaction, Grade 3: prolonged [e.g., not rapidly responsive to symptomatic medication and/or brief interruption of infusion]; recurrence of symptoms following initial improvement; hospitalization indicated for other clinical sequelae [e.g., renal impairment, pulmonary infiltrates]; Grade 4: life-threatening; pressor or ventilatory support indicated).

Immediately discontinue study drug infusion. Begin an IV infusion of normal saline, and treat the subject as follows. Recommend bronchodilators, epinephrine 0.2 to 1 mg of a 1:1,000 solution for subcutaneous administration or 0.1 to 0.25 mg of a 1:10,000 solution injected slowly for IV administration, and/or diphenhydramine 50 mg IV with methylprednisolone 100 mg IV (or

equivalent), as needed. Subject should be monitored until the Investigator is comfortable that the symptoms will not recur. Study drug will be permanently discontinued. Investigators should follow their institutional guidelines for the treatment of anaphylaxis. Remain at bedside and monitor subject until recovery from symptoms. In the case of late-occurring hypersensitivity symptoms (e.g., appearance of a localized or generalized pruritus within 1 week after treatment), symptomatic treatment may be given (e.g., oral antihistamine, or corticosteroids).

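### Section 4.3.1 B classes a Grade 3 infusion reaction that settles within 6 hours both as a DLT and as not a DLT, and states no order of precedence

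*Combined protocol and SAP*

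**What the plan says.** The lead-in to list B of Section 4.3.1 reads "Any of the following events will be considered a Non-Hepatic Non-Hematologic DLT", so each bullet is sufficient on its own. The second bullet names several Grade 3 drug-related events and ends with "infusion reaction of any duration requires discontinuation". The third bullet is the general rule for other Grade 3 or higher toxicity. It carries its own list of exceptions, the last of which is a "Grade 3 infusion reaction that returns to Grade 1 in ≤ 6 hours". Those exceptions are attached to the third bullet only.

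Section 3.6 refers back to 4.3.1 for the definition. Appendix 1 uses DLT counts without redefining a DLT. For Grade 3 or 4 infusion reactions, Section 4.3.7 says "Study drug will be permanently discontinued", with no time limit.

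**The concern.** A Grade 3 drug-related infusion reaction that is back to Grade 1 within 6 hours meets the second bullet and also meets the exception. Two sites could code it differently, and each could point to the text.

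The classification has uses beyond description. DLTs are named in the primary objective (Section 1.4.1). The escalation model is fitted to the 28-day DLT data (Appendix 1, Section 1.1). The expansion review counts toxicities that meet the same criteria against 33% (Sections 3.5 and 3.7). Infusion reactions are also a known event with this drug: Section 1.6 reports 6 of 34 subjects (17.6%) on monotherapy, although its dose breakdown of 1 + 3 + 3 adds to 7, and 14 of 50 (28%) on the combination.

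**Working it through.** **Can the text be read so that the conflict disappears?** Three readings were tried.

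1. *The second bullet covers only reactions that need discontinuation.* Section 4.3.7 requires permanent discontinuation after every Grade 3 or 4 infusion reaction, so every Grade 3 reaction still qualifies and the conflict remains.
2. *The second bullet is a management rule placed here by mistake.* It still sits under a lead-in that makes each bullet a DLT.
3. *One clause simply wins.* If any single bullet suffices, the 6-hour exception has no effect. If the specific clause overrides the general one, the words on duration have no effect for infusion reactions. Each choice empties a written clause, and the protocol makes neither.

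**Effect of one disputed event on the counts.** The inputs are cohorts of about 3 and a cap of 12 DLT-evaluable subjects per dose level (Section 8.1.1 and Appendix 1), six Part D cohorts and two Part E cohorts of about 40 each (Sections 3.1 and 8.1.2), and the 33% rule pooled over cohorts at the same dose (Section 3.7).

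- Escalation cohort of 3: 0/3 = 0% or 1/3 = 33.3%.
- Dose level at its cap: 1/12 = 8.3 points.
- Part D: 6 × 40 = 240 subjects, and 1/240 = 0.42 points.
- Part E: 2 × 40 = 80 subjects, and 1/80 = 1.25 points.

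At full enrolment in Part E, one event decides the 33% comparison only when the count already stands at the edge: 26/80 = 32.5% against 27/80 = 33.75%. The rule applies continuously, so an event weighs more while few subjects have been treated.

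**Effect on the dose recommendation.** The prior values are not in the available text, so the model cannot be re-run, and a substitute prior would not represent it. The protocol's own example is the best guide (Appendix 1, text on Figure 2). With 1/3 at 30 mg in combination, 240 mg and 800 mg are excluded (overdosing probabilities 0.384 and 0.595 against the cutoff of 0.35). The model still escalates to 100 mg, whose target probability of 0.311 exceeds 0.295 at 30 mg and 0.263 at 10 mg. Dose skipping is not allowed, so 100 mg was the highest next step in any case.

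**Did such an event occur?** Section 1.6 reports, for 34 Part A subjects at the December 2016 cut, no DLTs and no discontinuation for an adverse event attributed to study drug. The absence of DLTs alone proves little, because the exception could have removed the event from the count. The discontinuation statement is more informative: a related Grade 3 infusion reaction calls for discontinuation, so if the protocol was followed there was none. In Part B, the reactions described at 30, 100 and 240 mg resolved with oral acetaminophen, and the visible Grade 3 events at 100 and 240 mg include no infusion reaction. The four reactions at 800 mg have no visible detail.

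**The case against.** The strongest reply is that the second bullet speaks the language of patient management, while the third is the one that sets out DLT status with exceptions. On that view the protocol means: stop the drug after any Grade 3 infusion reaction, but do not count a short one as a DLT. This is workable, agrees with Section 4.3.7 and is probably what was intended. What stands is the direction of the fix. What does not stand is the claim that the text already says it, because the lead-in makes the second bullet a DLT criterion.

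The reply on consequences largely stands: the overlap concerns one event type, final dose choice rests on all available data, and passing 33% prompts discussion rather than an automatic stop.

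A reader might infer three stronger points, which the documents do not support.

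- *That dosing could resume after a short Grade 3 reaction.* Section 4.3.6 ties permanent discontinuation to "Any drug related AE occurring at any time that meets DLT criteria as outlined in" Section 4.3.1, and Section 4.3.5 opens with "Subsequent dosing with study therapy may resume once drug-related non-DLT AEs resolve to Grade 1 or baseline". Section 4.3.7 is introduced by "Treatment recommendations are provided below and may be modified based on local treatment standards". But the second bullet itself requires discontinuation at any duration, and 4.3.7 does so without a time limit. Permission to adapt treatment locally does not cancel the second bullet, so this route is largely closed.
- *That the exception also reaches bronchospasm and hypersensitivity, because 4.3.7 says of an infusion reaction that* "it might manifest with fever, chills, rigors, headache, rash, pruritus, arthralgias, hypo- or hypertension, bronchospasm, or other symptoms". The exception names infusion reactions only, and the second bullet lists the other two separately. Extending it would loosen the DLT rule.
- *That a disputed event was likely.* The rates of 17.6% and 28% cover all grades. No Grade 3 rate or time to recovery is given, so no probability of occurrence can be derived.

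**Conclusion.** The definition contradicts itself for one event type, and no other section resolves it. The point holds as a minor one. Its size is 0/3 against 1/3 in a single escalation cohort, 8.3 points at 12 subjects, about 0.4 points over Part D and 1.25 points over Part E. The expansion figures assume that the planned cohort sizes are reached and that the 33% rule pools cohorts at the same dose, as Section 3.7 words it.

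No affected event or altered dose decision is visible. The inference that Part A had none assumes that the discontinuation rules were followed. Part B cannot be settled fully, because the 800 mg reactions are not described in the available text. Nothing here supports saying that a dose was wrongly selected.

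**What to change.** In the second bullet of Section 4.3.1 B, after infusion reaction and for that term only, add: *except one that is back to Grade 1 within 6 hours, which is not counted as a DLT but still requires permanent discontinuation under Section 4.3.7*. Leave bronchospasm and hypersensitivity reaction as DLTs of any duration.

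In the study report, state that no such event occurred. If one did, give the DLT count and the final dose-toxicity model under both classifications.

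The cost is one clause and one reporting sentence, plus one refit of the final model only if an event is found. The downside is a slightly less conservative DLT count. Deleting the 6-hour exception is the conservative alternative and would also remove the conflict.
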